### **13.6            Confidentiality and Disclosure**

Any and all scientific, commercial, and technical information disclosed by Vertex in this protocol or elsewhere will be considered the confidential and proprietary property of Vertex. The investigator shall hold such information in confidence and shall not disclose the information to any third party except to such of the investigator's employees and staff as have been made aware that the information is confidential and who are bound to treat it as such and to whom disclosure is necessary to evaluate that information. The investigator shall not use such information for any purpose other than determining mutual interest in performing the study and, if the parties decide to proceed with the study, for the purpose of conducting the study.

The investigator understands that the information developed from this clinical study will be used by Vertex in connection with the development of the study drug and other drugs and diagnostics, and therefore may be disclosed as required to other clinical investigators, business partners and associates, the FDA, and other government agencies. The investigator also understands that, to allow for the use of the information derived from the clinical study, the investigator has the obligation to provide Vertex with complete test results and all data developed in the study.

### **13.7            Publications and Clinical Study Report**

---

### **13.7.2 Clinical Study Report**

A CSR, written in accordance with the current ICH E3 Guideline, will be submitted in accordance with local regulations.

3 MODIFICATIONS

3.1 Modifications to the Approved Clinical Study Protocol

Not applicable.

3.2 Modifications to the Approved Statistical Analysis Plan

Not applicable.

3.3 Modifications to the Approved IDMC Charter

[figure not shown]
Not applicable.

4 INTRODUCTION

This statistical analysis plan (SAP) describes the efficacy, safety, tolerability and is based on the most recent approved clinical study protocol (CSP), the most recent approved electronic case report form (eCRF), and the most recent approved eCRF completion guidelines. This SAP also documents analyses not specified in the protocol, which will provide supportive information for the scientific understanding of the drug entity.

All analysis outputs (tables, figures, listings, and datasets) will be generated using SAS® Version 9.4 or higher (SAS Institute, Cary, North Carolina, USA).

The SAP (Methods) will be finalized and approved before the clinical database lock. Any revisions to the approved SAP will be documented and approved in an amendment to the SAP prior to the clinical database lock. Any revisions made to the SAP after the clinical database lock will be documented in the clinical study report for this study.

5 STUDY OBJECTIVES

5.1 Primary Objectives

- To evaluate the efficacy of VX-864 on blood levels of functional alpha-1 antitrypsin (AAT) in individuals with the PiZZ genotype

5.2 Secondary Objectives

- To evaluate the efficacy of VX-864 on blood levels of antigenic AAT in individuals with the PiZZ genotype
- To evaluate the efficacy of VX-864 on blood levels of Z-polymer in individuals with PiZZ genotype
- To evaluate the efficacy of VX-864 on liver Z-polymer in individuals with the PiZZ genotype (in Group B only)
- To evaluate the safety and tolerability of VX-864 in individuals with the PiZZ genotype

6 STUDY ENDPOINTS

6.1 Primary Endpoints

- Change from baseline in blood levels of functional AAT at Week 48

6.2 Secondary Endpoints

- Change from baseline in blood levels of functional AAT over time
- Change from baseline in blood levels of antigenic AAT over time
- Change from baseline in blood levels of Z-polymer over time
- Change from baseline in Z-polymer accumulation in the liver over time (in Group B only)
- Safety and tolerability assessments based on adverse events (AEs), clinical laboratory values, standard 12-lead ECGs, and vital signs

7

STUDY DESIGN

7.1 Overall Design

This is a Phase 2, open-label, multicenter study. Approximately 20 subjects with the PiZZ genotype will be enrolled. Groups A and B will enroll approximately 10 subjects each. All subjects will receive VX-864 500 mg every 12 hours (q12h) for 48 weeks. Figure 7-1 displays the study design.

Group A subjects will not have a liver biopsy.

Subjects in Group B will have 2 liver biopsies performed over the course of the study. All liver biopsies will be performed percutaneously. All subjects in Group B (approximately 10 subjects) will have a liver biopsy during the Pretreatment Interval (Figure 7-1). Approximately 5 subjects (Group B1) will have a second liver biopsy at Week 24. Approximately 5 subjects (Group B2) will have a second liver biopsy at Week 48.

The pretreatment liver biopsy must be performed at least 7 days before Day 1 dosing, after all eligibility criteria have been met. Local laboratory hematology and coagulation results must be collected and reviewed by investigator within approximately 48 hours prior to the liver biopsy being performed. The Week 24 and Week 48 liver biopsies will be performed 3 hours (± 30 minutes) postdose relative to the morning dose.

The Safety Follow-up Visits are required for all subjects. For subjects who terminate their participation early, the ETT visit, which may be conducted at the site or by telephone or video interview, replaces the Day 28 Safety Follow-up Visit, if the ETT Visit occurs 3 weeks or later following the last dose of study drug. All subjects may also consent to the posttreatment Telemedicine Visit(s) following final dose of study drug, to monitor for development of AEs of rash (for up to 6 months) and to monitor any ongoing AEs of rash (for up to 6 months following resolution of AEs of rash; see Protocol Section 9.1.6).

Figure 7-1 VX22-864-108 Study Design

Treatment Period		
Day 1 to Week 48, VX-864 (N=20)		
Screening Up to 70 days before first dose ^a	Group A (n=10) No liver biopsy	Safety Follow-up 14 and 28 (± 2) days after last dose, and posttreatment telemedicine visit(s) ^c
Group B Pretreatment Interval Up to 14 days ^b before first dose	Cohort B1 (n=5) Liver biopsy at Pretreatment Interval and Week 24	
	Cohort B2 (n=5) Liver biopsy at Pretreatment Interval and Week 48	

[figure not shown]
n: size of subsample; N: number of subjects

Notes: Figure is not drawn to scale. Figure is not drawn to scale.

^a In subjects not requiring augmentation therapy washout, the Screening Period will be up to 28 days. In subjects requiring augmentation therapy washout, the Screening Period will be up to 70 days.

^b Day -14 to Day -7; pretreatment liver biopsy must be performed at least 7 days before Day 1 dosing.

^c There will be no further dosing in this study as of 25 September 2023. All subjects may consent to the posttreatment Telemedicine Visit(s) following final dose of study drug, to monitor for development of AEs of rash (for up to 6 months) and monitor any ongoing AEs of rash (for up to 6 months following resolution of AEs of rash; see Protocol Section 9.1.6).

7.3 Randomization

Not applicable.

7.4 Replacement

Subjects who withdraw or are withdrawn for non-safety reasons during the study drug treatment period may be replaced at Vertex's discretion. Refer to Section 9.10 of the CSP for more details.

7.5 Blinding and Unblinding

Refer to Section 10.7 of the CSP for details.

8 ANALYSIS SETS

The following analysis sets are defined: All Subjects Set, Full Analysis Set (FAS), and Safety Set (SS).

8.1 All Subjects Set

The **All Subjects Set** is defined as all subjects who were enrolled or received at least 1 dose of study drug. This analysis set will be used for individual subject data listings and disposition summary tables unless otherwise specified.

8.2 Full Analysis Set

The **Full Analysis Set (FAS)** is defined as all enrolled subjects who have received at least 1 dose of study drug. The FAS will be used to summarize background characteristics and for all efficacy analyses unless otherwise specified.

8.3 Safety Set

The **Safety Set (SS)** is defined as all subjects who have received at least 1 dose of study drug. The SS will be used for all safety analyses unless otherwise specified.

9 STATISTICAL ANALYSIS

9.1 General Considerations

The Schedule of Assessments is provided in Section 3 of CSP. The precision standards for reporting safety variables are provided in an internal Biometrics document that specifies the programming rules including the precision for derived variables.

Continuous variables will be summarized using the following descriptive summary statistics: the number of subjects (n), mean, SD, median, minimum value (min), and maximum value (max).

Categorical variables will be summarized using counts and percentages.

Baseline value, unless specified otherwise, will be defined as the most recent non-missing measurement (scheduled or unscheduled) collected before the first dose of study drug. For ECGs, the baseline value will be defined as the average of the non-missing pretreatment measurements (triplicate) on Day 1. For subjects who have ever been on augmentation therapy at any time, only functional and antigenic AAT levels collected during screening >42 days after the last dose of augmentation therapy can be used to define baseline values.

Change (absolute change) from baseline will be calculated as post-baseline value – baseline value.

Treatment-emergent (TE) Period will include the time from the first dose of study drug to 28 days after the last dose of study drug or to the completion of study participation (as defined in Section 9.1.8 of CSP), whichever occurs first.

Visit Window: The analysis visit windows for the protocol-defined visits are provided in Appendix A.

Unscheduled visits: Data obtained from unscheduled visits will be included in the analysis as follows:

- In scheduled visit windows per specified visit windowing rules
- In the derivation of baseline and last on-treatment measurements
- In the derivation of maximum and minimum values during TE period, and maximum and minimum change from baseline values during TE period for safety analyses
- In individual subject data listings as appropriate

Incomplete or missing data will not be imputed, unless specified otherwise.

Outliers: No formal statistical analyses will be performed to detect and/or remedy the presence of statistical outliers, unless specified otherwise.

All individual subject data will be presented in individual subject data listings based on the All Subjects Set.

9.2 Background Characteristics

9.2.1 Subject Disposition

Disposition summary will be provided by group and overall.

The number of subjects, based on the All Subjects Set, in the following disposition categories, will be summarized:

- All Subjects Set

- Full Analysis Set
- Safety Set
- Enrolled but not dosed

The number and percentage of subjects, based on the , in each of the following disposition categories, will be summarized:

- Completed treatment
- Discontinued treatment and the reason for discontinuation from treatment
- Completed study (i.e., completed Safety Follow-Up Visit or Post-treatment Telemedicine Visit)
- Discontinued the study and the reason for discontinuation from study

The corresponding data listing will also be provided.

9.2.2 Demographics and Baseline Characteristics

Demographics and baseline characteristics will be summarized based on the FAS by group and overall.

Demographic data will include the following:

- Age (in years)
- Sex (female and male)
- Ethnicity (Hispanic or Latino, not Hispanic or Latino, and not collected per local regulations)
- Race (White, Black or African American, Asian [Northeast Asian, Southeast Asian, Other Asian, Asian, Region Not Reported], American Indian or Alaska Native, Native Hawaiian or Other Pacific Islander, Other, and Not Collected per Local Regulations)

Baseline characteristics will include the following:

- Weight (kg)
- Height (cm)
- BMI (kg/m²)
- Prior Augmentation Therapy (Yes, No)
- Smoking History (Yes, No)

- ppFEV₁ category determined during the Screening Period or from historical data (< 50%, ≥50% and <80, ≥80%)
- ppFEV₁ obtained during the Screening Period or from historical data (%)
- FEV₁ obtained during the Screening Period or from historical data (L)
- FVC obtained during the Screening Period or from historical data (L)
- Ratio of FEV₁ and FVC obtained during the Screening Period or from historical data (%)
- Functional AAT level (μM)
- Antigenic AAT level (μM)
- Blood Z-polymer level (mg/L)
- Liver Z-polymer level (mg/L) (Group B only)

9.2.3 Medical History

Medical history will be coded by using the Medical Dictionary for Regulatory Activities (MedDRA). Medical history will be summarized descriptively based on the FAS by MedDRA system organ class (SOC) and preferred term (PT). This summary will be provided by group and overall.

9.2.4 Prior and Concomitant Medications

Medications will be coded using the World Health Organization-Drug Dictionary (WHODrug) and categorized as the following for the purpose of analysis:

Prior medication: Medication that started before the first dose of study drug

Concomitant medication: Medication continued or newly received during the TE Period

Post-treatment medication: Medication continued or newly received after the TE period.

A given medication may be classified as a prior medication, a concomitant medication, a post treatment medication, or more than one of these categories.

If a medication start date is on or after the first dose date of study drug, then the medication will be classified as a concomitant medication regardless of whether the medication end date is missing or not. If a medication end date is before the first dose date of study drug, then the medication will be classified as a prior medication regardless of whether the medication start date is missing or not. Note that a medication that started before the first dose of study drug and continued after the first dose will be classified as a prior medication and separately as a concomitant medication.

If a medication has a missing or partially missing start/end date and it cannot be determined whether it was taken before the first dose of study drug, or concomitantly, it will be classified as a prior and concomitant medication.

Missing or partial dates will be imputed for medications. Details for imputing missing or partial start and/or stop dates of medications are described in Appendix B.

Prior medications will not be summarized but will only be listed. Concomitant medications will be summarized based on the FAS by PT. This summary will be provided by group and overall.

Prior, concomitant, and post-treatment non-pharmacological therapy will be listed.

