#### **9.5            Prior and Concomitant Medications**

Information regarding prior and concomitant medications, including any AATD medications or therapies, other medications, and herbal and naturopathic remedies, will be collected in each subject's source documentation for medications taken within the 70 days before the first dose of study drug in this study through completion of study participation, as defined in Section 9.1.9.

- Subjects should stop augmentation therapy regimen for at least 42 days prior to level of antigenic AAT sample collection used to determine eligibility, and refrain from restarting augmentation therapy until 28 days after final dose of study drug.
- Subjects may receive doses of prednisone or prednisolone up to 5 mg/day chronically.
- Subjects may receive an acute course of corticosteroids (prednisone, prednisolone, hydrocortisone, or triamcinolone only) as standard of care to treat a PEx (dose and duration per investigator judgement in consultation with the Sponsor).
- Sedation and local anesthesia (e.g., midazolam, fentanyl, local lidocaine) used for the liver biopsy procedure (Group B only) are allowed. Low-dose non-nonsteroidal anti-inflammatory drug (NSAID) pain medications (e.g., acetaminophen with codeine, oxycodone, acetaminophen with oxycodone) are allowed for post-procedure pain. VX-864 may cause increased exposure of sensitive CYP3A4 substrates. When utilizing sensitive CYP3A4 substrates for sedation, local anesthesia, or acute pain management, caution should be utilized and dose adjustments may be considered.

Clinical experience suggests that VX-864 strongly inhibits CYP3A4 and may increase exposure of sensitive CYP3A4 substrates. Therefore, concomitant administration of sensitive CYP3A4 substrates are prohibited (Table 9-1). VX-864 is a mild inhibitor of organic anion transporting polypeptide 1B1 (OATP1B1) and as such use of OATP1B1 substrates are permitted (except when also a substrate of CYP3A4).

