Appendix B: Imputation Rules for Missing Prior/Concomitant Medication Dates

Missing or partial dates will be imputed for medication. Algorithm for missing or partial start date is:

- a. If day is missing, use the first day of the month;
- b. If month is missing, use January (1 January if day is also missing);
- c. If year is missing, no imputation is conducted.

Algorithm for missing or partial end date is:

- a. If day is missing, use the last day of the month;
- b. If month is missing, use December (31 December if day is also missing);
- c. If year is missing, no imputation is conducted.

Missing data algorithms will be reviewed to ensure the algorithms work. For example, end date will not be before the start date after the imputation.

In summary, the prior, concomitant, or post categorization of a medication is described below.

Table 12-2 Prior and Concomitant Categorization of a Medication

Medication Start Date	Medication Stop Date		
	< First Dose Date of Study Drug	≥ First Dose Date and ≤ End Date of TE Period	> End Date of TE Period
< First dose date of study drug	P	PC	PCA
≥ First dose date and ≤ End date of TE Period	-	C	CA
> End date of TE period	-	-	A

C: Concomitant; P: Prior; A: Post

Imputation rules for missing and/or partial dates of non-pharmacological treatment/procedure will follow the same imputation rule.

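### One sentence in SAP 9.2.4 makes every medication started on or after first dose concomitant, with no end date, and so conflicts with the definition in the same section and with Table 12-2

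*SAP*

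**What the plan says.** SAP 9.2.4 first defines the classes by period of use: "Concomitant medication: Medication continued or newly received during the TE Period" and "Post-treatment medication: Medication continued or newly received after the TE period". It allows overlap: "A given medication may be classified as a prior medication, a concomitant medication, a post treatment medication, or more than one of these categories". It then gives date rules. One of them says that if a medication's "start date is on or after the first dose date of study drug, then the medication will be classified as a concomitant medication", whether or not the end date is missing. That rule does not mention the end of the TE Period.

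Appendix B closes with Table 12-2, introduced by "In summary, the prior, concomitant, or post categorization of a medication is described below". The table crosses start date with stop date. For a start after the TE Period, the only filled cell is under the stop-date column "> End Date of TE Period", and it holds A (post) alone.

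SAP 9.1 runs the TE Period from "first dose of study drug to 28 days after the last dose of study drug or to the completion of study participation", whichever comes first. Under SAP 9.2.4, concomitant medications are tabulated by preferred term on the Full Analysis Set, by group and overall. Prior medications are only listed. No summary table is specified for post-treatment medications.

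**The concern.** For a medication that starts after the TE Period, the sentence gives one class and the definition and table give another. A programmer and an independent validator could each follow the SAP and produce different concomitant-medication tables.

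Such records can exist in this trial. Protocol 9.5 collects medications through completion of study participation. Under Protocol 9.1.9, for subjects who stop drug early without withdrawing consent, that can run to the last telemedicine visit. Protocol 9.1.6 places that visit up to 6 months after last dose, or up to 6 months after a rash resolves. Dosing stopped for everyone on 25 September 2023 (Protocol 9.6.1), so any subject then on treatment stopped early.

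The boundary also falls where restrictions lift. Protocol 9.5 tells subjects to "refrain from restarting augmentation therapy until 28 days after final dose of study drug", which is nominally the day on which the TE Period ends. Several other restrictions in Protocol Table 9-1 end at the same point. The planned table has no timing dimension, so a permitted later restart could not be told apart in it from use inside the restricted period.

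**Working it through.** There is no sample size or power figure to reproduce. The check sets the rules side by side.

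**Inputs.** TE end = last dose day + 28, assuming participation has not ended sooner (SAP 9.1). The rules compared are:

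1. the date sentences of SAP 9.2.4 read literally;
2. the same sentences plus the section's own post-treatment definition;
3. the definitions in SAP 9.2.4 alone;
4. Table 12-2.

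Last-dose days of 28, 84 and 168 were assumed, and all three gave the same result. P = prior, C = concomitant, A = post. An ongoing medication is treated as stopping after the TE Period.

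| Start, stop | (1) | (2) | (3) | (4) |
|---|---|---|---|---|
| Before first dose, before first dose | P | P | P | P |
| Before first dose, within TE Period | PC | PC | PC | PC |
| Before first dose, ongoing | PC | PCA | PCA | PCA |
| Within TE Period, within TE Period | C | C | C | C |
| Within TE Period, ongoing | C | CA | CA | CA |
| Last day of TE Period, ongoing | C | CA | CA | CA |
| TE end + 1 day, ongoing | C | CA | A | A |
| Last dose + 90 days, ongoing | C | CA | A | A |
| Last dose + 90, last dose + 120 | C | CA | A | A |
| Last dose + 180 days, ongoing | C | CA | A | A |

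The definitions and Table 12-2 agree on all 10 patterns. The sentence disagrees with Table 12-2 on concomitant status in the 4 patterns that start after the TE Period, and in none of the other 6. Adding the post-treatment definition (column 2) does not help, because the C remains.

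**Worked example.** Last dose on day 84 gives a TE end of 84 + 28 = day 112. Augmentation restarted 90 days after last dose starts on 84 + 90 = day 174, which is after day 112. The sentence makes it concomitant. Table 12-2 makes it post-treatment only.

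**Time exposed.** A subject who consents to telemedicine follow-up and is followed for the full 6 months, about 26 weeks, has 26 − 4 = 22 weeks of post-dose recording in which a new start is classed differently. A subject who completes treatment finishes participation at the last Safety Follow-up Visit, 28 (±2) days after last dose, so has at most about 2 such days.

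**Size per record.** With the planned 20 subjects, one such record adds at most 1/20 = 5 percentage points to a row of the overall column. With about 10 planned per group, it adds at most 1/10 = 10 points to a group column. These are planned numbers; the actual size of the Full Analysis Set is not in the documents.

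**After the fix.** With the sentence limited to starts on or before TE end, concomitant status matches Table 12-2 in all 10 patterns.

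**The case against.** The best defence is that the sentence was meant for something narrower. It ends by dealing with missing end dates, and its neighbours concern the boundary between prior and concomitant, so it reads as a missing-date rule for that boundary. The definition above it and the summary table in Appendix B agree with each other, and a careful programmer would follow them. This stands as an account of how the wording arose, and it makes the consequence conditional. It does not remove the conflict, because the sentence is a direct instruction in the body of the SAP and nothing says that Table 12-2 takes precedence. The overlap allowance does not reconcile them either, since the table cell is A and not CA.

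A reader might infer that augmentation resumed months later would appear as on-treatment use of a prohibited therapy and so cloud the primary outcome. The documents do not support that:

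- Concomitant means use within the TE Period, which already includes up to 28 days off drug.
- Medication class enters no efficacy analysis that can be read. The protocol's primary model has visit as its only fixed effect. SAP 9.3.2 summarises the blood endpoints descriptively. The SAP's primary-analysis text is partly blacked out, so nothing is claimed about it.
- SAP Appendix A limits the on-treatment efficacy windows to assessments no later than 1 day after last dose, and Protocol Table 3-4 shows no AAT sample at the telemedicine visits.
- Subject-level listings are planned, and important deviations are identified under a separate plan (SAP 9.2.6), so a permitted restart would not become a recorded deviation because of this sentence.

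A restart on or before the last day of the TE Period is concomitant under every rule, so the fix does not change it.

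**Conclusion.** The inconsistency is real and minor. The unbounded sentence cannot be followed together with the TE-Period definition and Table 12-2 for any medication that starts after the TE Period. If it is programmed literally, those medications enter the concomitant-medication summary as if used within the TE Period. The effect stops at that descriptive table.

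The size cannot be fixed from the documents, because the number of such records is not given and could be zero. The 22-week figure assumes consent to telemedicine and the full 6 months of follow-up. The figures of 5 and 10 percentage points assume the planned enrolment.

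**What to change.** In SAP 9.2.4, limit the sentence to start dates on or after first dose *and on or before the end of the TE Period*. Add that a medication starting after the end of the TE Period is post-treatment only, as in Table 12-2. A statement that Table 12-2 governs would be a weaker substitute, because it leaves the conflicting sentence in place.

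The cost is one clause and one sentence. Data collection, analysis sets and clinical conduct do not change. Under SAP Section 4, the change goes in as an amendment before database lock, or is documented in the clinical study report if made after it.
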